## 4 Analysis Plan

For all of the above objectives, targeted minimum loss-based estimation (TMLE) will be used to estimate the mean counterfactual outcome for the population of interest, under each treatment, and at each time point (3 months and 6 months). For binary variables we will estimate the proportion or probability of the outcome.

### 4.1 Notation and Causal Estimands

The following notation will be used to denote study data:

- $A$ : randomized treatment assignment at baseline
- $Y_j$ : outcome of interest at the  $j$ th time point
- $W_0$ : patient baseline covariates
- $\Delta_{Yj}$  whether or not  $Y_j$  was measured for the patient (1 = observed, 0 = missing)

The subscript  $j$  will take on values 0, 1, 2, to denote data collected at baseline, 3 months and 6 months, respectively. We assume that the observed data may be represented sequentially for the three month outcome as  $O_1 = (W_0, A, \Delta_{Y,1}, \Delta Y_1)$  and for the six month outcome as  $O_2 = (W_0, A, \Delta_{Y,2}, \Delta Y_2)$ .

In order to define our causal estimands of interest, we use counterfactual notation. Counterfactual notation describes the outcome a participant would have under a specified intervention (even if that intervention was not observed for the patient). We denote this outcome as  $Y(a)$  to represent the outcome under treatment  $A = a$ . Our estimands of interest generally take the form  $E[Y(1) - Y(0)]$  which is the expected difference in the average outcome if everyone in the population took treatment one versus treatment zero. We use the following notation to describe the assigned treatments:  $(a_1)$  control,  $(a_2)$  P3 and P3+,  $(a_{2a})$  P3, and  $(a_{2b})$  P3+. Table 6 outlines the estimands of interest for each study objective. Note that since a patient

Table 6: Estimands of Interest.

Study Objective	Estimand a	Comparison	Outcome(s)
Primary	$P[Y(a_2)] - P[Y(a_1)]$	Average effect of P3/P3+, compared to SOC	Protective levels of TFV-dp and FTC-tp in DBS
Secondary I	$P[Y(a_{2a})] - P[Y(a_1)]$	Average effect of P3 compared to SOC	Same as primary
	$P[Y(a_{2b})] - P[Y(a_1)]$	Average effect of P3+ compared to SOC	
Secondary II	$P[Y(a_2)] - P[Y(a_1)]$	Average effect of P3/P3+ compared to SOC	Self-reported weekly PrEP use Self-reported monthly PrEP use
Secondary III	$P[Y(a_2)] - P[Y(a_1)]$	Average effect of P3/P3+ compared to SOC	Panel of self-reported outcomes
Cost	$\frac{E[C(a_{2b}) - C(a_{2a})]}{E[Y(a_{2b}) - Y(a_{2a})]}$	Ratio of expected cost difference to expected efficacy difference between P3+ and P3	C will be calculated cost and Y will be the outcome of interest for assessing treatment efficacy

a The difference in notation between  $P$  and  $E$  represents whether the estimand is a difference in proportions or a difference in mean outcomes, respectively.

cannot theoretically receive both P3 and P3+ as treatment, the counterfactual outcome under treatment ( $a_2$ ) represents the average counterfactual outcome of patients under P3 and P3+.

In order to estimate the estimands in table 3, we may use our observed data and, under certain assumptions, obtain estimates via the g-formula (see Supplement for details) and TMLE.

## 4.2 TMLE Analysis for Average Causal Effects

TMLE, combined with super learning, will be used to address both the primary and secondary study objectives. The regression models needed for TMLE estimation include the propensity for treatment, the propensity for missingness, and the outcome regression. We will use super learning to estimate these regressions. Super learning is a machine learning method that, when given a set of modeling algorithms, uses cross-validation to determine the optimal convex combination of the algorithms. This allows us to combine flexible learners with more traditional methods (linear/logistic regression) to create our models, and thereby improves the chances that the models are specified correctly. The details for building each regression are given below.

### Estimating Propensities

The probability of treatment assignment at baseline is essentially known since this is a randomized trial. Therefore, we will use simple empirical means to estimate the probability of treatment  $A = a$ . Using the notation  $\bar{g}_a$  to denote the propensity for treatment  $a$  we may write.

$$\bar{g}_{a,n} = \frac{1}{n} \sum_{i=1}^n I(A = a)$$

Where the subscript n is added to indicate that this is an estimator of  $\bar{g}_{a,0}$ .

Unlike treatment assignment, the propensity of missing a follow-up time point is not randomized and may be estimated with parametric models or via data adaptive methods. From henceforth, we will denote the propensity of having data at follow-up time point j, as  $\bar{g}_{\Delta_{Y_j}}(a, w_0) = P(\Delta_{Y_j} = 1 | W_0 = w_0, A = a)$ , where  $j = 1, 2$  and  $a$  is the treatment regimen of interest. To create this model, we will regress  $\Delta_{Y_j}$  on baseline patient covariates and dummy variables for each possible treatment group. For baseline patient covariates, we will use age, baseline DBS data, baseline PrEP use (yes or no), site, and race/ethnicity. We will employ super learning with a candidate library to estimate the propensity for missingness. See table 7 for candidate algorithms and the variables considered.

#### *Estimating Outcome Regressions*

In order to estimate the mean counterfactual outcome via the g-formula, we must estimate an outcome regression. Suppose our objective has K treatments of interest then  $k = 1, 2, \dots, K$ . Let  $k$  denote the  $k^{th}$  treatment of interest. The necessary regression for the outcome at time point j,  $j=1,2$ , takes the following form:

$$\bar{Q}_k^j(w_0) = E(Y_j | A = a_k, \Delta_{Y_j} = 1, W_0)$$

Similar to our approach to propensity score estimation, we will estimate this regression with super learning and will include all treatment interventions  $A$ , by incorporating a dummy variable for each possible intervention (except control group which will be the reference group). Each regression will be fit on a subset of data where  $\Delta_{Y_j} = 1$ . The baseline covariates included will be age, DBS, PrEP use, site, and race/ethnicity. See table 7 for the super learner libraries and variables included.

Once these regressions are fit, we use the TMLE estimator of average treatment effect (ATE) to obtain our final estimates for the counterfactual outcomes of interest. For additional details regarding the regressions fit, super learning, TMLE, and variance estimation please refer to the Supplement. For the primary objective please also refer to section 7.2 and Supplement A.5 for additional considerations regarding the TMLE analysis.

### 4.3 Hypothesis Tests and Multiple Testing Adjustment

Table 8 lists the hypotheses to be tested for each study objective. Each hypothesis comparing P3/P3+ to SOC will be tested at both 3 and 6 months, separately. For comparisons of P3 vs SOC and P3+ vs SOC, we will report the comparisons in a descriptive manner as opposed to conducting additional hypothesis tests (i.e. Secondary objectives I, II, and III).

Table 8 lists the p-value adjustment for each hypothesis test. For the primary objective no adjustment is done. For secondary objective II, a Bonferroni Correction will be applied to adjust for multiple testing and to maintain a nominal alpha level of approximately 0.05 within the objective. Due to the exploratory nature of secondary objective III, we will use a Benjamini-Hochberg adjustment, which controls the false discovery rate (FDR). We will use 0.20 as the desired FDR, which is the proportion of rejected null hypotheses that are actually true (See Glickman, 2014 for more information).

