10.2.3 RCT Power Considerations

[figure not shown]
A total of 240 participants will be enrolled at baseline to account for a 20% expected loss to follow-up during the first 3 months of the study leaving an estimated 192 individuals (64 per arm) for analysis. Power was assessed via Monte Carlo simulation. Data were simulated as follows. A single binary baseline variable W was drawn from a Bernoulli (1/2) distribution to represent patient-level characteristics included in the analysis. A binary intervention variable A was drawn from a Bernoulli (2/3) distribution to mimic the 1:1:1 treatment allocation. A binary intermediate variable I_1 was drawn from a Bernoulli (3/4) distribution to mimic participant app utilization. A censoring variable C_1 for the month three visit was drawn from a Bernoulli (1/20) distribution, with the value 1 indicating a participant was lost-to-follow-up before the three-month visit. For uncensored participants, PrEP adherence at month three Y_1 was drawn from a Bernoulli distribution with adherence probability equal to $\text{logit}^{-1}(-1 + \beta_1 A)$. Thus, approximately 27% of participants in the SOC arm were assumed to be adherent at the three-month visit. Note that the parameter β_1 describes the log-odds-ratio of adherence comparing treatment to SOC. Next, we drew L_2 from a Bernoulli (3/4) distribution to mimic participant app utilization after the three month visit, and drew C_2 from a Bernoulli (1/20) distribution, where again a value of 1 indicated a participant was lost-to-follow-up between the three- and six-month visit. For uncensored participants, PrEP adherence at month six Y_2 was drawn from a Bernoulli distribution with adherence probability equal to $\text{logit}^{-1}(-1.5 + \beta_2 A + 1.5 Y_1)$. Thus, approximately 18% of participants in the SOC arm who were not adherent at month three, were adherent at month six, while 50% of participants in the SOC arm who were adherent at month three were again adherent at month six. Note that the parameter β_2 describes the log-odds-ratio of adherence at month six comparing treatment versus control for participants with the same month three adherence.

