# 1 Revision History

Version	Date	Summary of Changes
Final	05-JAN-2022	
Amendment 1	07-JULY-2022	
Minor Changes Throughout: Updates to notation to maintain consistency. Also added/removed and changed sentences as necessary to improve the organization of the protocol.
 
Section 3.1 (see also Table 4, 8, and 10)

	04-MARCH-2022	Changed the primary study objective to consider FTC-tp and TFV-dp levels in the blood separately.
	28-JAN-2022	
Section 3.2 (see also Tables 5, 6, 8, and 12)
 Removed secondary objective II, where FTC-tp and TFV-dp were analyzed as continuous outcomes.
	13-APR-2022	Added self-reported weekly and monthly PrEP use as outcomes of interest for the secondary study objective.
	10-JAN-2022	Added exploratory outcomes as determined by the study team.
	10-JULY-2022	
Section 3.3 (see Table 6)
 Updated the cost effectiveness objective to reflect that it is a comparison between P3 and P3+ as originally defined in the protocol.
	09-MARCH-2022	
Section 4.2 (see Table 7)
 Updated super learner libraries. We added a simple model and regularization models (glmnet and stepwise selection) out of concern regarding the large number of confounders in our models.

	26-JUNE-2022	Removed statement regarding double robustness of TMLE.
	13-APR-2022	Added race/ethnicity to the variable list.  Section 4.3 (see also Table 8)
	13-APRIL-2022	Hypothesis testing for 3 and 6 months was separated into two different hypothesis tests as opposed to considering a joint test of no treatment effect at both 3 and 6 months. This effects the primary and secondary/exploratory objectives.  Section 4.4
	13-JULY-2022	Added this section to explain cost analysis.  Section 6.1
	25-JUNE-2022	Timeline updated to reflect realized dates  Section 6.2
	16-MARCH-2022	Updated the imputation steps for missing survey data.  Section 6.3
	13-APR-2022	Race/ethnicity was added as a confounder to control for in all analyses (see also Table 7).  Section 6.4
	21-JUNE-2022	Removed longitudinal TMLE as a sensitivity analysis for unmeasured, time-varying confounding.  Supplement
	09-MARCH-2022	Added a sensitivity analysis for the primary objective.
	21-JUNE-2022	Rewrote the supplement to provide adequate detail regarding the TMLE procedure for incorporating survey data into the analysis of the primary objective.

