### 4.4 Cost Analysis

Cost was reported at the site-level. To calculate the incremental cost effectiveness ratio we assigned to each participant the average cost per person at their study site and within their treatment arm. We treated this value as if it was the participant's realized cost. This was then used in a complete case analysis comparing the mean cost difference between participants on P3+ vs P3 divided by the mean efficacy difference as measured by the binary TFV measure at 3 months. To create a 95% confidence interval we used the percentile bootstrap method.

Table 7: Super Learner Libraries and variables used for the propensity score and outcome regressions

Model	Outcome	Learner(s)	Baseline Variables 
$\bar{g}_{\Delta Y_j}(a, w_0)$	Self-Reported PrEP use or Exploratory Outcome of Interest Observed	SL.glm	BEO  , BEO*trt
			Age, BEO, On PrEP, Site, Race/Ethnicity
		SL.earth	Age, BEO, on PrEP, Site, Race/Ethnicity, (BEO * On PrEP), (Age*trt)
			Age, BEO, on PrEP, Site, Race/Ethnicity
		HAL	Age, BEO, on PrEP, Site, Race/Ethnicity
		glmnet	Age, BEO, on PrEP, Site, Race/Ethnicity, (BEO * On PrEP), (Age*trt)
$\bar{Q}_k^j(w_0)$	Self-Reported PrEP use or Exploratory Outcome	SL.glm	Age, BEO, on PrEP, Site, Race/Ethnicity, (BEO * On PrEP), (Age*trt)
			Age, BEO, on PrEP, Site, Race/Ethnicity
		SL.earth	Age, BEO, on PrEP, Site, Race/Ethnicity
			Age, BEO, on PrEP, Site, Race/Ethnicity
		HAL	Age, BEO, on PrEP, Site, Race/Ethnicity
		glmnet	Age, BEO, on PrEP, Site, Race/Ethnicity, (BEO * On PrEP), (Age*trt)
Treatment		step	Age, BEO, on PrEP, Site, Race/Ethnicity, (BEO * On PrEP), (Age*trt)

trt -

Treatment

BEO - Exploratory measure at baseline

 Baseline variables to include in the model, in addition to dummy variables for treatment

 If the outcome of interest is available at baseline, it will be controlled for. If not, another variable may be controlled for, if it is predictive for both the EO and missingness.

Table 8: Hypotheses and P-Value Significance Thresholds

Study Objective	Hypothesis	Significance Threshold
Primary	There is no difference between P3/P3+ and SOC in terms of PrEP adherence, as measured by binary FTC-tp.	0.05
	There is no difference between P3/P3+ and SOC in terms of PrEP adherence, as measured by binary TFV-dp.	
Secondary II	There is no difference between P3/P3+ in terms of self-reported weekly PrEP use.	0.025

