	There is no difference between P3/P3+ in terms of self-reported monthly PrEP use.	
Secondary III	There is no difference between P3/P3+ and SOC in terms of self-reported outcome.	Benjamini-Hochberg

Table 9: Baseline variables stratified by treatment group (Table 1)

Variable	P3 (N= )	P3+ (N= )	SOC (N= )
Symmetric Baseline Variables, mean (SD)			
Skewed Baseline Variables, median (Q1,Q3)			
Categorical Baseline Variables, count (%)			

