## 6 General Considerations and Statistical Issues

### 6.1 Timeline

1. Data Available: February 24, 2022
2. Analysis Done: April 20, 2022
3. Manuscript Complete: TBD

Table 11: Estimated difference in proportion of protective PrEP use between treatment groups and SOC group, where P3 and P3+ are considered separately (table 3)

P3 vs. SOC	Estimated Difference	95% CI
Protective PrEP Level in Blood: TFV-dp		
3 months		
6 months		
P3+ vs. SOC	Estimated Difference	95% CI
Protective PrEP Level in Blood: TFV-dp		
3 months		
6 months		
P3 vs. SOC	Estimated Difference	95% CI
Protective PrEP Level in Blood: FTC-tp		
3 months		
6 months		
P3+ vs. SOC	Estimated Difference	95% CI
Protective PrEP Level in Blood: FTC-tp		
3 months		
6 months		

Table 12: Estimated difference in self-reported PrEP use between treatment groups and SOC group.

P3/P3+ vs SOC	Estimated Ratio	95% CI	p-value
Self-reported Weekly PrEP Use			
3 months			
6 months			
Self-reported Monthly PrEP Use			
3 months			
6 months			
P3 vs SOC	Estimated Ratio	95% CI	
Self-reported Weekly PrEP Use			
3 months			
6 months			
Self-reported Monthly PrEP Use			
3 months			
6 months			
P3+ vs SOC	Estimated Ratio	95% CI	
Self-reported Weekly PrEP Use			
3 months			
6 months			
Self-reported Monthly PrEP Use			
3 months			
6 months			

Table 13: Estimated difference in proportions (or mean outcomes) between treatment group and SOC group for self-reported exploratory outcomes (table 5)

P3/P3+ vs SOC	Estimated Difference	95% CI	p-value
Outcome 1			
3 months			
6 months			
Outcome 2			
3 months			
6 months			

Table 14: Frequency of Missing Data, in entire cohort and by treatment group, reported as count (%). (table 7)

Variable	Total (N= )	P3 (N= )	P3+ (N= )	SOC (N= )
Baseline data				
Baseline Variables				
3 month data				
TFV-dp				
FTC-tp				
Outcome 1				
...				
Outcome p				
6 month data				
TFV-dp				
FTC-tp				
Outcome 1				
...				
Outcome p				

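### Secondary objective II: the 0.025 threshold corrects for two tests, but the SAP plans four

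*SAP*

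**What the plan says.** SAP 4.3 sets the testing rule for comparisons of the pooled intervention arms with standard of care: "Each hypothesis comparing P3/P3+ to SOC will be tested at both 3 and 6 months, separately". For secondary objective II it then says that "a Bonferroni Correction will be applied to adjust for multiple testing and to maintain a nominal alpha level of approximately 0.05 within the objective".

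Table 8 lists two hypotheses for this objective, "There is no difference between P3/P3+ in terms of self-reported weekly PrEP use" and "There is no difference between P3/P3+ in terms of self-reported monthly PrEP use", with a threshold of 0.025. The comparator is missing from that wording, but Table 6 shows that it is standard of care.

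The shell for the results is "Table 12: Estimated difference in self-reported PrEP use between treatment groups and SOC group". Its P3/P3+ versus SOC block has a p-value column with four rows: weekly use at 3 and 6 months, and monthly use at 3 and 6 months. The blocks for P3 and P3+ taken singly have no p-value column, and 4.3 makes those comparisons descriptive, so they add no tests.

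**The concern.** The family that 4.3 undertakes to protect is the whole objective, and the objective contains four tests. The threshold in Table 8 allows for two. Nothing in the SAP brings the count down: it defines no separate error budget for each visit, sets no testing order, and does not require significance at both visits.

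The text and the table can therefore give different answers. A p-value between 0.0125 and 0.025 is significant by Table 8 but not by the Bonferroni rule described in 4.3. Two analysts who each follow the SAP could report different conclusions on self-reported adherence.

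**Working it through.** **Inputs.** Target error for the objective: about 0.05 (SAP 4.3). Outcomes: 2 (Table 8). Visits, tested separately: 2 (SAP 4.3). Threshold per test: 0.025 (Table 8). Tests are taken as two-sided; Protocol 10.3.3 says so for the primary tests, and the SAP is silent for this objective.

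**The plan's own figure.** 0.05/2 = 0.025, so Table 8 is reproduced exactly with two tests. The guarantee is then 2 × 0.025 = 0.05, or 1 − 0.975² = 0.0494 if the two tests are independent. That is the error at one visit.

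**The tests actually planned.** 2 outcomes × 2 visits = 4.

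- Guaranteed bound at 0.025: 4 × 0.025 = 0.10.
- Independent tests at 0.025: 1 − 0.975⁴ = 0.0963.
- Bonferroni threshold for four tests: 0.05/4 = 0.0125.
- Guaranteed bound at 0.0125: 4 × 0.0125 = 0.05.
- Independent tests at 0.0125: 1 − 0.9875⁴ = 0.0491.

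**Allowing for correlation.** The documents give no correlations, so the values below are assumptions. The four test statistics were simulated as multivariate normal with no true effect (4 million draws). Their correlation matrix is the Kronecker product of a between-measure and a between-visit matrix. The last column is the share of trials in which the two thresholds disagree on whether anything is significant.

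| Measures | Visits | Any significant at 0.025 | Any significant at 0.0125 | Disagree |
|---|---|---|---|---|
| 0.9 | 0.9 | 0.0515 | 0.0271 | 0.0244 |
| 0.9 | 0.7 | 0.0615 | 0.0324 | 0.0291 |
| 0.9 | 0.5 | 0.0666 | 0.0348 | 0.0318 |
| 0.9 | 0.3 | 0.0695 | 0.0360 | 0.0334 |
| 0.7 | 0.5 | 0.0790 | 0.0412 | 0.0378 |
| 0.5 | 0.3 | 0.0889 | 0.0460 | 0.0429 |
| 0 | 0 (exact) | 0.0963 | 0.0491 | 0.0472 |

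Weekly and monthly use are overlapping recalls of the same behaviour, so the rows with measures correlated 0.9 are the likelier ones. The rate at 0.025 falls below 0.05 only at extreme correlation: about 0.043 with both correlations at 0.95, and 0.046 to 0.050 if the two measures are perfectly correlated and the visits correlated 0.5 to 0.

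**Power cost of 0.0125.** A test with 80% power at 0.025 has a standardised effect of 2.241 + 0.842 = 3.083. At 0.0125 the critical value is 2.498, so power is P(Z > 2.498 − 3.083) = 0.721.

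Protocol 10.2.3 plans for losses "leaving an estimated 192 individuals (64 per arm) for analysis", which gives 128 versus 64. The standard error in SD units is √(1/128 + 1/64) = 0.1531. The difference detectable with 80% power rises from 3.083 × 0.1531 = 0.47 SD to (2.498 + 0.842) × 0.1531 = 0.51 SD.

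**The case against.** The best defence is that 0.025 was meant to control error at each visit. Table 8 lists two hypotheses, 4.3 tests them separately by visit, and 0.05/2 is exactly right for one visit. The documents do not show which statement is the slip. Declaring a family per visit would also have been a legitimate choice in advance. But 4.3 names the objective as the family, and no other text narrows it. Adopting the per-visit reading now would loosen the stated guarantee after the analysis.

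The second defence is that the text promises only approximate control and the tests are positively correlated. This has some force. With measures correlated 0.9 and visits 0.7 or higher, the actual rate at 0.025 (0.052 to 0.062) is nearer to 0.05 than the rate at 0.0125 (0.027 to 0.032). The figure of 0.10 is a bound, not an expected rate. However, Bonferroni is used because its guarantee needs no knowledge of the correlations, and a guarantee of 0.10 is not approximately 0.05.

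The revision history says that testing was "separated into two different hypothesis tests as opposed to considering a joint test of no treatment effect at both 3 and 6 months", which might suggest a threshold that was never updated. It appears to date that split and the addition of the two self-report outcomes to the same day, 13 April 2022, so it does not settle where 0.025 came from. The finding rests on the current text alone.

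The SD figures depend on an unadjusted comparison of means. For this objective Table 6 uses the notation for proportions and Table 12 is headed as a ratio, so the scale is itself unsettled. The drop from 80% to 72% power does not depend on the scale.

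**Conclusion.** The inconsistency is real. Table 8 divides correctly but counts two tests where the plan has four, so the guaranteed bound within the objective is 0.10 rather than 0.05. Under the assumed correlations the error at 0.025 runs from about 0.052 to 0.096, and the two thresholds disagree in 2.4% to 4.7% of trials with no effect.

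The severity is minor. Protocol 2.2 uses the self-reported measures to see whether they agree with the primary results, all four p-values are to be reported, and the primary tests are untouched.

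**What to change.** Set the Secondary II threshold in Table 8 to 0.05/4 = 0.0125 for each of the four tests, which carries out the rule 4.3 already states. SAP 6.1 records "Analysis Done: April 20, 2022", so state openly that the correction came after the analysis. Report all four p-values and mark any between 0.0125 and 0.025 as meeting only the threshold previously in Table 8.

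Do not move to Holm at this stage. Its last step is 0.05, looser than 0.025, so a p-value such as 0.04 could become newly significant if the other three tests had passed.

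The work is one table cell, one sentence of disclosure and a flag in the results table. The change can remove a significant result but never add one; the price is the power loss shown above.
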